#### 7.1.2 Secondary Endpoints

Consistent with the secondary study objective to assess the acceptability of, and adherence to, a short term regimen of 0.5% PRO 2000/5 Gel (P), the following endpoints will be assessed:

• The proportion of participants who were "adherent" to the product use regimen, as defined in Section 4.5.

• The proportion of participants who at their Day 14 Follow-up Visits report via questionnaire that they would be "completely unwilling" to use 0.5% PRO 2000/5 Gel (P) during sexual intercourse in the future.

Consistent with the secondary study objective to evaluate aspects of product acceptability, the following endpoints will be assessed (via questionnaire and focus group discussions):

- Reported positive aspects of using PRO 2000/5 Gel (P).
- Reported negative aspects of using PRO 2000/5 Gel (P).

Consistent with the secondary study objective to assess the feasibility of this population for enrollment in future PhaseII/III vaginal microbicide studies, the following endpoint will be assessed:

• The proportion of participants who at their Day 14 Follow-up Visit report via questionnaire they would be willing to participate in future phase II/III vaginal microbicide trials.

Consistent with the secondary study objective to assess the effect of a twice daily short-term regimen of 0.5% PRO 2000/5 Gel (P) on the vaginal microflora of sexually active HIV-uninfected women in Pune, India, the following endpoint will be assessed:

• The Gram stain scores at enrollment, and follow-up (Days 2, 7 and 14).

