# **1.2.2** Clinical Research

Phase I clinical trials to evaluate the safety and tolerance of intravaginal PRO 2000/5 Gel (P) in healthy, sexually abstinent volunteers were conducted in Antwerp, Belgium and London, England [13]. In these randomized, double-blind, placebo-controlled studies, a total of 73 women were enrolled across both sites and asked to apply placebo (N=25), 0.5% (N=24) or 4% (N=24) PRO 2000/5 Gel (P) intravaginally once per day for two weeks between menses. Sterile, preservative-free gels were used in these trials.

All women enrolled in the placebo and 0.5% groups completed two-weeks of dosing. Three women in the 4% group withdrew because of, respectively: (1) vaginal burning and gastrointestinal symptoms, (2) vulvar ulcers (not evaluated for HSV), genital irritation and gastrointestinal symptoms, and (3) intermenstrual bleeding (28 months after discontinuation, this subject was diagnosed with invasive cervical carcinoma judged unrelated to product use).

No serious adverse events were reported during either trial. Cervical abrasion was observed colposcopically in 3 subjects (2 in the 4% group and 1 in the placebo group) after 14 days of product use, while cervicovaginal ulceration was not seen in any subject during product use. Intermenstrual bleeding (usually "spotting") was reported by participants across all dose groups, and usually resolved with continued dosing. Histological evaluation of vaginal biopsies showed mild or moderate inflammatory cell infiltration in 5/36 baseline and 5/35 post-treatment samples (London cohort only); 4 participants (2 in the 4% group and 2 in the placebo group) showed treatment-emergent increases in these inflammatory signs. Neither laboratory safety tests or nor direct analysis of plasma drug levels showed evidence for systemic absorption of PRO 2000/5. Microscopic evaluation of vaginal swab specimens collected 12 hours after the last gel application indicated that product use had no impact on the normal vaginal ecology (London cohort only). Discharge due to gel expulsion was common across all dose groups. Overall, PRO 2000/5 Gel (P), at both concentrations, was found to be generally well tolerated, with promising local and systemic safety profiles. There were fewer genital adverse events in the placebo and 0.5% groups than in the 4% group.

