A subsequent Phase I clinical trial was conducted within the HIV Prevention Trials Network to evaluate the safety, tolerance and acceptability of PRO 2000/5 Gel (P) in healthy, sexually active women at low-risk for HIV/STD infection and asymptomatic, sexually abstinent, HIV-infected women. The study was conducted at two sites in South Africa (Durban and Johannesburg) and two in the United States (Providence, RI and Philadelphia, PA).

In the first part of this open-label study, successive cohorts of about 12 healthy, HIV-uninfected women at low-risk for HIV/STD infection were asked to apply 2% or 4% PRO 2000/5 Gel (P) intravaginally once or twice daily for 14 consecutive days between menses. These participants agreed to engage in vaginal intercourse at least two times per week with a single, monogamous male partner using non-spermicidally lubricated or unlubricated male condoms.

Following interim analysis of the preliminary safety data from these cohorts, a Safety Review Committee determined the highest tolerated dose and dose frequency [4% PRO 2000/5 Gel (P) twice daily], which was then evaluated in a cohort of asymptomatic, HIV-infected women who were sexually abstinent over the two-week dosing period. Subjects underwent baseline pelvic, colposcopic, and laboratory exams, and were re-examined after 7 and 14 days of product use. Acceptability assessments were also performed at baseline and follow-up.

A total of 50 HIV-uninfected and 13 HIV-infected volunteers were enrolled in the study. The product was well tolerated by both populations: no serious adverse events were reported, and 100 percent of the women responding to a post-study questionnaire indicated they would be willing to use the product again if it were shown to protect against HIV.

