#### 3.4 Participant Withdrawal

Once a participant has enrolled in the study, the study site will make every reasonable effort to retain her for the 14-day study follow-up period. Given the relatively small study sample size, and the importance of ascertaining all safety outcomes among study participants, 100 percent retention of enrolled participants is targeted. Study site staff are responsible for developing and implementing local standard operating procedures to achieve complete follow-up.

However, participants may withdraw from the study for any reason at any time. The Investigator also may withdraw participants from the study in order to protect their safety and/or if they are unwilling or unable to comply with required study procedures. Participants also may be withdrawn if the study sponsor or US or Indian regulatory authorities terminate the study prior to its planned end date.

Every reasonable effort will be made to complete a final evaluation of participants who terminate from the study prior to Day 14, and study staff will record the reason(s) for all withdrawals from the study in participants' study records.

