#### 4.6 Toxicity Management

In response to AEs reported by study participants and/or observed upon exam by study staff, the investigator or designee will recommend either continuation or discontinuation of product use consistent with the criteria in Appendix III. Product use also will be discontinued in the event of pregnancy.

Participants who discontinue product use will not routinely be withdrawn from the study. Rather, every effort will be made to complete the safety evaluations scheduled to take place on study Days 7 and 14.

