# 5.6.1 Clinical Procedures

- Update locator information.
- Administer Follow Up Acceptability Assessment.
- Review Daily Study Records and note the time of last product application.
- Count the number of used and unused product tubes and conduct adherence interview. Store used tubes until end of study. If space does not allow storage then document the count and disposal.
- Collect urine for leukoesterase screen (if symptomatic) and culture if screen positive for WBCs.
- Perform pelvic examination with colposcopy (according to Appendix V) including:
  - > speculum examination of vagina and cervix,
  - colposcopic examination of the vaginal and cervical mucosa for lesions,
  - take colposcopic digital image(s) without filter, encompassing the cervix and fornices,
  - collect pH sample from vaginal wall,
  - Collect swab from anterior or lateral fornix for:
    - one dried smear (smear specimen on slide and allow to air dry),
    - wet prep (two samples of discharge on slide for saline prep, potassium hydroxide prep and whiff test),
  - bimanual examination for adnexal masses or tenderness.
  - if abnormal vaginal discharge or purulent cervicitis is noted, collect urine for *N. gonorrhoeae* and *C. trachomatis* LCR assay.
  - ➢ if ulcerative lesions are noted:
    - photograph lesions according to procedures in Appendix V.
    - collect swabs for syphilis dark field microscopy (on-site) and M-PCR for HSV-2, *H. ducreyi* and *T. pallidum*. (at the HPTN Central Lab)
- If symptomatic, collect urine for dipstick urinalysis.
- Provide instruction for follow-up care as appropriate.
- Collect blood specimens for hematology, liver and renal function, APTT/PT and PRO 2000/5 analysis.

- Instruct participant to contact or return to the study site if she experiences discomfort, discolored or malodorous discharge, or other AEs within the next week.
- Schedule focus group visit.
- Label digital image with location/image number.
- Complete all required data collection forms.

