#### 7.4 Data Analysis

Statistical analyses, described in Sections 7.4.1 and 7.4.2, will be performed using the SAS® and StatXact statistical software packages. As noted above, all analyses will include available data on all 60 study participants. When the use of descriptive statistics is required, the following methods will be used: for categorical variables, the number and percent in each category, with exact confidence intervals for the proportions; for continuous variables, the mean, median, standard deviation, quartiles, and range (minimum, maximum). Changes from baseline to follow-up will be analyzed using McNemar's test (for categorical response variables) or the paired t-test (for continuous response variables. A summary of the analysis tables that will be created is provided in Appendix VIII.

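### The unwillingness-to-use endpoint rests on a questionnaire scheduled only at Day 14, so a woman who leaves earlier because of the gel cannot be counted as unwilling

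*Protocol*

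**What the plan says.** **The endpoint.** Protocol Section 7.1.2, under the first secondary objective, lists adherence and then "The proportion of participants who at their Day 14 Follow-up Visits report via questionnaire that they would be" completely unwilling to use the gel during intercourse in future. The report must be made by questionnaire at the Day 14 visit.

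**When the questionnaire is given.** Section 5.6.1 lists "Administer Follow Up Acceptability Assessment" among the Day 14 procedures. No other follow-up visit in Section 5 or Appendix I has it. The Letter of Amendment of 3 November 2003 deleted the enrollment questionnaire, so Day 14 (allowable Days 12 to 16, Section 5.6) is now the only visit with an acceptability questionnaire.

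**Women who leave early.** Section 3.4 states: "Every reasonable effort will be made to complete a final evaluation of participants who terminate from the study prior to Day 14". It requires reasons for withdrawal to be recorded but does not list the contents of that evaluation. The same section says that "100 percent retention of enrolled participants is targeted".

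**Women who stop the gel but stay.** Section 4.6: "Participants who discontinue product use will not routinely be withdrawn from the study". The follow-up effort named there is for the Day 7 and Day 14 safety evaluations.

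**Analysis.** Section 7.4 says that "all analyses will include available data on all 60 study participants", with exact confidence intervals for proportions. It gives no rule for a woman without a Day 14 questionnaire.

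**The concern.** Leaving a study because of the product is itself evidence about acceptability. The women most likely to answer that they are completely unwilling include those who leave because of local symptoms, discharge or a partner's objection. The endpoint can only be met by someone who attends Day 14 and completes the form, so such a woman cannot enter the numerator. Any error from this source runs one way, towards a more favourable figure.

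At stake is one descriptive secondary proportion, not the safety objective. The matter still belongs in the protocol. An analysis plan can set a denominator or a missing-data rule, but it cannot recover an answer that nobody was asked to give.

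**Working it through.** **1. Is there a stated figure to reproduce?** None for acceptability. The table in Section 7.2 concerns toxicity. Its 5% row checks: 1 − 0.95^60 − 60 × 0.05 × 0.95^59 = 0.808, against the stated .81. It neither supports nor weakens this point.

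**2. How is an early leaver counted?** Take a woman with no Day 14 questionnaire.
- If available data means women who answered, she is dropped from numerator and denominator.
- If the denominator is all 60, she stays in it and is counted as not unwilling.

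On neither reading is she counted as unwilling.

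**3. Size.** Let *u* be the women answering completely unwilling at Day 14, and *d* the women who left earlier because of the gel and would have given that answer. With 60 enrolled (Section 7.2):
- as written, available data: *u* / (60 − *d*)
- leavers counted: (*u* + *d*) / 60
- difference: (*d* / 60) × (1 − *u* / (60 − *d*))

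If the denominator is held at 60, the difference is exactly *d* / 60, or 1.67 points per leaver.

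The protocol gives neither *u* nor *d*. Both are assumed below, with Clopper-Pearson 95% intervals.

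| *u* | *d* | As written | Leavers counted | Difference (points) |
|---|---|---|---|---|
| 0 | 0 | 0/60 = 0% (0 to 6.0) | 0/60 = 0% (0 to 6.0) | 0 |
| 0 | 2 | 0/58 = 0% (0 to 6.2) | 2/60 = 3.3% (0.4 to 11.5) | 3.3 |
| 0 | 3 | 0/57 = 0% (0 to 6.3) | 3/60 = 5.0% (1.0 to 13.9) | 5.0 |
| 0 | 5 | 0/55 = 0% (0 to 6.5) | 5/60 = 8.3% (2.8 to 18.4) | 8.3 |
| 3 | 1 | 3/59 = 5.1% (1.1 to 14.1) | 4/60 = 6.7% (1.8 to 16.2) | 1.6 |
| 3 | 3 | 3/57 = 5.3% (1.1 to 14.6) | 6/60 = 10.0% (3.8 to 20.5) | 4.7 |
| 3 | 6 | 3/54 = 5.6% (1.2 to 15.4) | 9/60 = 15.0% (7.1 to 26.6) | 9.4 |

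Per leaver this is 1.6 to 1.7 points for *u* from 0 to 3.

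**4. Does the background suggest a value for *d*?** Only loosely. Section 1.2.2 reports 3 withdrawals among 73 women in the trials in abstinent women, and 4 product discontinuations among 63 women in the later Phase I trial. Scaled to 60 these are 60 × 3/73 = 2.5 and 60 × 4/63 = 3.8, so about 2 to 4 women and 3 to 7 points. That holds only if such women also missed Day 14 and would all have been unwilling. The three withdrawals were all at the 4% strength ("Three women in the 4% group withdrew because of" symptoms or bleeding). None of the 24 women on 0.5%, the strength used here, failed to complete dosing, although that regimen was once daily and without intercourse.

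**5. Does anything else in the plan correct the proportion?**
- Positive and negative aspects (Section 7.1.2) are separate endpoints. Focus groups and their one-on-one, telephone or written alternatives (Section 5.8) are voluntary, and transcripts are analysed qualitatively (Section 7.4.2). Scheduling the focus group is a Day 14 task (Section 5.6.1).
- Adherence (Section 4.5) registers some leavers but not all. Missing doses on three or more days without an adverse event that requires stopping makes a woman non-adherent. A woman who stops for such an event after full dosing is classed as adherent.
- Adverse events leading to discontinuation (Section 7.4.1), and completion with day of discontinuation (Appendix VIII, table 1), are tabulated separately.

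These keep product-related exits visible, but none of them enters the unwillingness proportion.

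**The case against.** The best case on the other side has three parts.

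**The early evaluation may already include the questionnaire.** Section 2.3 calls Day 14 the final study follow-up visit, so a final evaluation before Day 14 could be read as that visit brought forward. A Study-Specific Procedures Manual, not shown, may say so. This is a fair reading, and the protocol does not rule it out. But the protocol does not state it either, and the endpoint would still refer to a report made at the Day 14 visit.

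**Missing-data rules belong in the analysis plan.** This is right for the denominator and for sensitivity analyses, and their absence alone would be no defect. It does not cover who is given the form and when, which the protocol fixes.

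**The loss may be nil.** Follow-up lasts 14 days, full retention is targeted, women who stop the gel stay in the study and can answer at Day 14, and partners must consent before enrollment. All of this stands, and it limits the size of the problem.

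A reader might also draw stronger conclusions that the documents do not support:
- *That acceptability as a whole is judged only from Day 14 answers.* Positive and negative aspects are also assessed through focus groups and their alternatives, and Appendix I offers a focus group or interview within four weeks of finishing the product.
- *That the earlier Phase I trial shows this bias at work.* Its report that "100 percent of the women responding to a post-study questionnaire indicated they would be willing to use the product again" is indeed among responders. But the four women who discontinued product are not said to have left the study or failed to respond, and their reasons include herpes cervicitis, a pregnancy at enrollment and a urinary tract infection.
- *That the gel will look more acceptable than it is.* That depends on a number of early leavers that the protocol does not give.

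**Conclusion.** The point holds in limited form and is a minor improvement. As written, the unwillingness endpoint can count only women who answer at Day 14. A woman who leaves earlier because of the gel has no scheduled opportunity to answer and is not counted as unwilling under either denominator. The direction of any resulting error is clear: unwillingness would be understated.

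The size rests on assumptions. It is about 1.6 to 1.7 points per leaver if each would have answered completely unwilling and 0 to 3 others did; less if some leavers would have answered otherwise; and zero at full retention. The sample size and the primary safety analysis are unaffected.

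**What to change.** - **Sections 3.4, 5.6.1 and Appendix I:** give the existing Follow-up Acceptability Questionnaire at Day 14 or at the final evaluation for early terminators, whichever comes first.
- **Section 7.1.2:** reword the endpoint so that a report at either occasion counts.
- **Reporting:** state how many women have no questionnaire.
- **Sensitivity count:** over all women who used the gel, show the proportion again with those who left for a recorded product-related reason, and have no questionnaire, classed as unwilling. Section 3.4 already requires the reasons to be recorded.

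The cost is a few lines of text and a few more questionnaires, with no new instrument or visit. The figure may turn out slightly less favourable. The sensitivity count treats leaving as a stated attitude, which is a deliberate worst case, so it should stand beside the main result and not replace it.

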#### 7.3 Data Monitoring

Close collaboration among protocol team members will be necessary to evaluate study progress and respond to occurrences of toxicity in a timely manner. Rates of accrual, adherence, follow-up, and AE incidence will be monitored closely by the protocol team on a regular basis. The team will meet via conference call every two weeks during the period of study implementation, and additional ad hoc calls will be convened if required.

The Site Investigator is responsible for continuous close monitoring of all AEs that occur among study participants, and for alerting the rest of the protocol team if unexpected concerns arise. All concerns then will be addressed according to DAIDS and HPTN standard operating procedures. In particular, for this study, accrual will be suspended if two or more study participants experience a grade 3 or higher AE (as defined by the DAIDS Standard Toxicity Tables) judged possibly, probably, or definitely related to product use. The protocol team then will review all pertinent safety data and determine whether to continue accrual and product use. A decision to stop the study may be made by the protocol team at this time, or at any such time that the team agrees that an unacceptable type and/or frequency of AEs has been observed.

#### 7.4 Data Analysis

Statistical analyses, described in Sections 7.4.1 and 7.4.2, will be performed using the SAS® and StatXact statistical software packages. As noted above, all analyses will include available data on all 60 study participants. When the use of descriptive statistics is required, the following methods will be used: for categorical variables, the number and percent in each category, with exact confidence intervals for the proportions; for continuous variables, the mean, median, standard deviation, quartiles, and range (minimum, maximum). Changes from baseline to follow-up will be analyzed using McNemar's test (for categorical response variables) or the paired t-test (for continuous response variables. A summary of the analysis tables that will be created is provided in Appendix VIII.

